### **I. Project Summary and Project Goals**

Sexual assault of college women is a serious and complex public health problem: one in five college women report being sexually assaulted. The purpose of this study is to conduct a randomized controlled trial study with 750 female college students from three universities to test the efficacy of RealConsent-F, a sexual violence risk reduction program for college women, compared to an attention-placebo comparison condition. The primary outcome will be self-reported sexual violence victimization and the secondary outcomes will be alcohol and dating protective- and risk-related behaviors and resistance strategies. Our expected outcomes are demonstrated feasibility and efficacy of a technologically novel risk reduction program for female college students.

### **II. Rationale and Background Information**

Epidemic of Sexual Violence Against College Women: Recent statistics on sexual violence against women in college have revealed a serious and complex public health problem: 6% of female college students report experiences of rape each year and one in five women report that she was sexually assaulted while in college. Assaults typically occur during freshman or sophomore year and, in most cases (75-80%), women state that they know their attacker, whether as an acquaintance, classmate, friend or (ex)boyfriend. Many women report experiencing an “incapacitated assault” meaning they were sexually abused while they, the victims, were drugged, drunk, passed out, or otherwise incapacitated. These data demonstrate the high level of sexual assault occurring among young adult college women. To reduce incidence rates, comprehensive approaches involving evidence-based, easily-disseminated educational products are greatly needed by institutions of higher learning to prevent male perpetration and reduce risk of sexual assault among women; however, evidence-based prevention and risk reduction programming is greatly lacking.

In 2014 the Centers for Disease Control and Prevention (CDC) conducted a review of 140 published sexual violence primary prevention interventions and concluded *only three* were

effective in preventing sexual violence perpetration. [Note: RealConsent male version (RealConsent-M) was not included in this review as the publication was “in press” at the time the review was conducted]. Of the three effective programs, none were specific to college students. To reduce sexual violence perpetration, best practices for prevention entail theoretically-driven activities that focus on improving 1) knowledge of consent and understanding the impact of alcohol; 2) addressing hyper-male ideology; 3) reducing hostility toward women; 4) reducing adherence to prescribed gender roles; 5) changing social norms to reduce acceptance of sexual violence; 6) dispelling rape myths; and 7) enhancing communication skills between men and women around sex. RealConsent-M incorporated segments that addressed all seven best practices. Using a randomized controlled trial (RCT), RealConsent-M demonstrated significant reductions in sexual violence perpetration; thus, RealConsent is the first effective prevention program for male college students.

### III. Methods

This study plans to conduct a randomized controlled trial with 750 female freshmen between 18-20 years of age from three universities in the state of Georgia (n=250 from each school) to test the efficacy of RealConsent-F compared to an attention-placebo comparison condition. Inclusion criteria for all proposed research activities are: female, aged 18-20 years, full time freshman, and single. Exclusion criteria are: other education levels, married, and/or graduate status. Participants will be randomized to either the intervention or attention-placebo study conditions. To control for Hawthorne effects, women in the RCT will be compared to women in an attention- placebo control condition—a general health promotion web-based program called “Stress Management.” Below are descriptions of the intervention, RealConsent and the attention-placebo program.

#### RealConsent-F

RealConsent includes 18 of 40 well-known behavioral change techniques. The program 1) provides information on the targeted behavior; 2) provides instruction on how to perform the behavior; 3) demonstrates or models the behavior; 4) demonstrates positive outcomes for engaging in the behavior or negative outcomes for failing to change behavior; and 5) provides encouragement and positive feedback as reinforcement. RealConsent-F uses didactic methods involving presentation of material via video; problem-based learning via quizzes with interactivity; short videos and animation to model the behavior. RealConsent-F is unique in that it includes serial drama episodes (i.e. “Squad”) featuring four college women going through their freshman year and experiencing issues related to alcohol use, sexual assault, stalking, and dating violence. This program is grounded in *educational entertainment* to provide educational content within entertainment programming (e.g., Sesame Street or Law and Order).

### Attention-Placebo Condition

*Stress Management* was developed by ISA Group ([www.isagroup.com](http://www.isagroup.com)) and is a multi-media web-based program designed to help manage stress levels. The program is dynamic and interactive with substantial use of video/audio. Each of 4 program modules is  $\approx 30$  minutes involving interactive and didactic activities. Thus, it approximates RealConsent-F in format and duration.

### Recruitment of N=750 Female College Freshmen

We have agreements with each of the three colleges to test RealConsent-F among female freshmen and they have agreed to provide a list of female students. We will send out email invites from [name]'s email account to a random sample of 500 students per school to ask for their participation in a research project. To control for demand characteristics, we will blind participants to the research question and indicate the purpose is to "test multimedia, web-based interactive programs designed for female college students." If the first round of 500 emails does not produce a 50% response rate, we will send out another batch of 500 email invites to reach our target goal of  $n=250$  at each college. [name] used this recruitment strategy for testing RealConsent-M. Female freshmen who are interested in the research will be able to access our online eligibility screener through a hyperlink in the body of the email that takes them to our study website. [name], a computer scientist and programmer, will develop the study website and a web-based application that will help our project director with recruitment and retention efforts. [name] developed a website and app for [name]'s current online study of 1,800 male freshmen.

### Informed Consent

The website will provide a short description of the study and, if interested, participants can click on a button to assess their eligibility followed by the informed consent process. The informed consent process is a crucial aspect of any study, but especially so when conducting web-based research involving sensitive topics. Special consideration must be made to ensure that participants are aware of their rights as participants in such research. A hyperlink will be displayed following the eligibility screener directing eligible participants to the informed consent form. Those not eligible will receive a message saying they are not eligible. An interactive process will be designed to secure informed consent. As part of registration, we will collect name, preferred email, mailing address, and cell phone number to maximize retention although identifying information will not be linked with survey data. The web app will allow us to collect key data for CONSORT. All participants are eligible to receive up to \$105 in Amazon e-gift cards for completing RealConsent-F and all surveys, which in our experience of 10 years of conducting online studies is feasible and necessary.

## Baseline Assessment, Randomization, and Completion of RealConsent or Stress

### Management:

Once a participant is registered, she will get a confirmation email; her response will trigger another email that contains a link to the online baseline survey and a password for accessing. To enhance confidentiality of responses, we will encourage participants to choose a private location, use a secure, encrypted Internet connection, and close their web-browser after they have completed a survey. Once an individual completes the baseline survey, she will be randomized using an automated stratified block randomization program to either RealConsent-F or to Stress Management programs. Stratified block randomization will ensure equal numbers between conditions and that 125 participants from each university are assigned to each condition.

We will communicate to the research participants and encourage them to complete their assigned task (RealConsent-F or Stress Management) within two weeks. Participants can complete the modules at their own pace within the 2-week window and are able to leave a module and finish it later. Email prompts will be sent every 48 hours to remind participants to complete the modules. Participants will be contacted by email and/or text message prior to 6 months post-intervention (Spring 2019) to complete the posttest.

### Retention Activities

Based on the experience and expertise of [name] and her team, we will employ a number of activities to maximize retention. In a preliminary study of N=1,153 college male freshmen assessed three times over 12 months, [name] and colleagues implemented activities to enhance recruitment: 1) sending touch-point emails in between assessments; 2) enabling participants to update changes in contact information via the web application; 3) providing full incentive amount for those who completed assessments on time as a “bonus;” 4) sending email and text reminders prior to due dates; and 5) emailing, texting and making phone calls up until final date. Our response rates were: 80% at wave 2 (6-months), and 81% at wave 3 (12-months). To ensure we maintain at least 80% retention rate, we will employ these strategies and those used previously by [name] in other studies involving follow-up assessments of adolescents and adults.

### Study Measures

The table below displays the measures that will be used in all study assessments.

**Table 1. Measures of Study Variables**

| Variable                                 | Measure  | # Items | <math>\alpha</math> |
|---|---|----------------|----------------------------|
| Primary Outcome:
Sexual Victimization | Revised Sexual Experiences Survey-SFV (SES)  | 35             | .74                        |
| Secondary Outcomes:
Dating behaviors  | The Dating Behavior Survey (DBS)          | 15             | .67                        |

|  |  |    |     |
|--|--|----|-----|
|  | The Dating Self-Protection Against Rape Scale  | 15 | .88 |
| Alcohol Protective Behaviors             | Protective Behavioral Strategies Survey        | 15 | .94 |
| Use of resistance tactics                | Use of Resistance Tactics                         | 6  | n/a |
| Mediators:                        |  |    |     |
| Alcohol use                              | Weekly Drinking and Heavy Episodic Drinking    | 2  | n/a |
| Perceptions of Alcohol-Related Risk      | Likelihood of nonconsensual sex due to alcohol    | 1  | n/a |
| Alcohol Expectancy                       | Revised Alcohol Expectancy Questionnaire       | 40 | .72 |
| Alcohol Use Norms                        | Drinking norms rating form                     | 1  | n/a |
| Bystander Behavior                       | Bystander Behavior Scale                                       | 10 | .89 |
| Knowledge of legal definitions of rape   | Legal Knowledge Scale                             | 7  | .69 |
| Perceptions of informed consent          | Informed Consent Index                            | 14 | n/a |
| Empathy for rape victims                 | Rape Empathy Scale                                | 19 | .84 |
| Communication with partner about sex     | Communication subscale of SSBQ                    | 7  | .80 |
| Sexual Assertiveness                     | Sexual Communication Survey                       | 10 | .90 |
| Self-efficacy to discuss sex             | Communication Self-Efficacy                       | 4  | .84 |
| Self-efficacy to use assertive responses | Self Efficacy Scale                               | 7  | .97 |
| Use of risk reduction strategies         | Personal and Social Risk Reduction Strategies Scale            | 34 | n/a |

#### IV. Safety Considerations

There are some potential risks for participating in the RealConsent program. Participants may experience some adverse psychological reactions such as feeling upset or discomfort as they undergo the intervention modules. For example, a potential risk is that a participant may gain a new awareness of an unwanted sexual experience that hitherto she thought of as “her fault for getting drunk”, but she now may indicate she was a victim of date rape. Although these instances represent some degree of risk, we have designed the procedures to minimize adverse reactions. Our project director, [name] [name] will conduct a check-in with each participant after completion of each intervention module. Participants can freely elect to terminate participation in the Web-based intervention if so desired. We anticipate that some participants may require counseling and we will be prepared to help these participants with appropriate referrals. [name] has extensive experience in addressing participants’ concerns during randomized trials will also undergo training by [name] and if needed, the principal investigator will address adverse reactions should they arise. Also, we will include on our study website a ([name]) number that can be accessed 24/7 for immediate crisis counseling in GA (GA Crisis and Access Line): [http://www.armstrong.edu/Departments/counseling\\_center/counseling\\_georgia\\_crisis\\_and\\_access\\_line](http://www.armstrong.edu/Departments/counseling_center/counseling_georgia_crisis_and_access_line)).

Another potential risk for participating is the administered assessments that may cause some participants to experience adverse psychological reaction such as distress, discomfort, or anxiety responding to explicit questions regarding their unwanted sexual experiences. We will state explicitly that participants can refuse to answer any questions, decline to answer any questions, or be allowed to skip any questions of the survey; they can also elect to terminate their participation immediately. The project director will be prepared to provide resources for participants should they request a referral, or as they respond to explicit questions regarding their unwanted sexual experiences.

One last risk entails a loss of confidentiality. A number of steps will be taken to secure sensitive data. These include the required use of personal identification numbers, access codes, and passwords on the study web site and on all web-administered surveys and assessments. Only the PI and the project director will have access to the online survey data through our Qualtrics account. Qualtrics web-survey platform employs a high level of data encryption. We will also secure the web site, which will deliver the RealConsent program. All data and recruitment materials will be stored on the PI's password-protected desktop located in her locked office at GSU.

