### Statistical Analysis

The complex empirical methods described below will be conducted by [name], an experienced statistician and colleague of [name]. Data analysis will be performed using the SAS Software System. Descriptive statistics for all measurements will be estimated and reported. Frequency distributions will be created to screen for any errors and will be used to summarize categorical data; measures of central tendency and dispersion will be used to summarize continuous data. All data will be examined for bivariate relationships and results used to build a multivariate statistical model.

We will analyze our study data with an intent-to-treat and per protocol analyses. An intent-to-treat analysis includes all participants who were randomized, regardless of compliance, withdrawal, and anything that happens after randomization. An advantage is that it is an analysis based on original randomization; however, effect estimation may be conservative and misleading with increasing attrition. A per protocol analysis considers only participants who fully complied and completed the study. Per protocol is less conservative and may reflect true treatment differences for those with full compliance. Including an intent-to-treat and per protocol analysis will provide a more complete understanding of treatment effects. Because we will most likely encounter incomplete data due to dropouts and non-response, multiple imputation of missing data will be used to impute missing values based on other available covariates.

Outcomes, including victimization and frequency of risky dating behaviors and alcohol-protective behaviors will be modeled using a general linear mixed model. This is an appropriate statistical model to use with repeated measures data collected over time. A random effect for subject will be included to account for the multiple measurements taken at baseline and 6-month follow-up on each subject. Treatment group and demographics will be included as fixed effects in the model. Mediation models will be tested with a two-tiered approach for mediation testing, with bootstrapping to generate estimates of the indirect effect and 95% confidence intervals.

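### The only check-in with a fixed trigger follows each completed intervention module, most naturally RealConsent-F, so distress may be found more often in that arm and women who stop mid-module are missed

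*Combined protocol and SAP*

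**What the plan says.** IV. Safety Considerations opens its first paragraph with "There are some potential risks for participating in the RealConsent program" and describes distress that may arise during the modules. As a safeguard, the project director "will conduct a check-in with each participant after completion of each intervention module". The term *intervention module* is not defined. The next paragraph names a second source of distress, shared by both arms: "Another potential risk for participating is the administered assessments that may cause some participants to experience adverse psychological reaction".

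III. Methods uses *intervention* for one arm: "Participants will be randomized to either the intervention or attention-placebo study conditions. To control for Hawthorne effects". The control condition was chosen to match attention. Its description says "Each of 4 program modules is" about 30 minutes long, and concludes: "Thus, it approximates RealConsent-F in format and duration".

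The other contacts in the program window are these:
- The section on baseline assessment and randomization says "Email prompts will be sent every 48 hours to remind participants to complete the modules". These are completion reminders, sent within a 2-week window.
- VI. Quality Assurance, item 3 of the adverse-event procedures, adds email and text contact, partly to check in and partly to promote compliance. It is not limited to one arm and has no schedule.

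VI. Quality Assurance also requires a written log of all events, immediate notification by the project director, a report on each adverse event within 10 days, and DSMB review of serious event reports and of risk against benefit. The fields of the log are not listed. The Statistical Analysis section covers efficacy: "Outcomes, including victimization and frequency of risky dating behaviors and alcohol-protective behaviors will be modeled using a general linear mixed model". It does not mention adverse events.

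**The concern.** A check-in finds distress that would otherwise go unreported. If one arm has a triggered contact and the other has only unscheduled contact, the same true distress can give different logged counts. The project director both makes the check-ins and must report adverse events, so what the check-ins find enters the adverse-event record.

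If logged events are later counted by arm, an excess in RealConsent-F could come from closer watching, and a real excess could be dismissed as closer watching. The plan does not require the log to show how an event was found, so the information needed to separate the two is not guaranteed to exist.

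Two further points do not depend on any count. The trigger is completion, so a woman who stops a module because it upset her does not set it off. And staff contact in one arm only works against the attention match that the control program is meant to provide.

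**Working it through.** **1. Which arm is checked?** For RealConsent-F only: the paragraph's subject is RealConsent, and III. Methods contrasts intervention with attention-placebo. For both arms: the sentence says each participant, and the section on baseline assessment speaks of modules for both programs. The phrase used for the control's modules does not help, because the documents call RealConsent a program too. The one-arm reading is the more natural, but it is not certain.

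**2. Which distress can the check-in reach?** The baseline survey comes before randomization, the modules fall in the next 2 weeks, and the posttest is at 6 months. A post-module check-in can pick up distress from the modules and any that lingers from the baseline survey. It would not normally pick up posttest distress.

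**3. Illustration of size.** The plan gives no figure on this point. From the documents comes only the arm size, 750/2 = 375. All rates below are assumptions: true distress 5% in both arms (range 3% to 10%); detection 80% with the triggered check-in; detection 40% without it (range 20% to 80%, where 80% means that both arms are checked or that the other contact works equally well).

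Logged rate = true rate × detection.

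| Case | RealConsent-F | Control | Difference | Fisher rejection, two-sided .05 |
|---|---|---|---|---|
| Central | 0.05 × 0.8 = 4.0% (15 of 375) | 0.05 × 0.4 = 2.0% (7.5 of 375) | 2.0 points | 30% |
| Half of distressed RealConsent-F women stop before finishing a module | 0.05 × (0.5 × 0.8 + 0.5 × 0.4) = 3.0% | 2.0% | 1.0 point | 10% |
| Upper end | 0.10 × 0.8 = 8.0% | 0.10 × 0.2 = 2.0% | 6.0 points | 97% |
| Equal detection | 2.4%, 4.0% or 8.0% | the same | 0 | about 3% to 4% |

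The logged ratio equals the detection ratio: 0.8/0.4 = 2.0 in the central case, and from 0.8/0.8 = 1.0 to 0.8/0.2 = 4.0 over the range. The last column shows only what would happen if an analyst chose to test the counts; the plan names no such test.

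**4. Precision of a by-arm table with equal detection.** The 95% half-width is 1.96 × √(2p(1 − p)/375): 2.2 points at p = 2.4%, 2.8 at 4% and 3.9 at 8%. Such a table can describe, but can settle little.

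**The case against.** The strongest reply is that an undefined term calls for clarification and does not demonstrate a bias. The sentence says each participant, the arm-neutral email and text contact may detect equally well, and the DSMB reviews risk against benefit. Much of this stands. A reader might infer that the documents establish a one-arm check-in; they do not. But the both-arms reading still leaves women who stop mid-module without a trigger, and neither the email and text contact nor DSMB review sets a schedule or a standard question.

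A second reply is that the harm falls on an analysis that is not planned: the plan contains no between-arm adverse-event comparison. That is also right. A reader might infer that a false safety signal will arise, or that unequal detection could never be recognised. The text supports less. Each event is investigated and reported, and unspecified log fields do not show that arm and source go unrecorded, only that recording them is not required.

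A reader might also infer that survey distress in general is found unevenly. Posttest distress lies outside the check-in window, and the section on safety handles survey distress without regard to arm, by letting women skip questions or withdraw and by offering resources.

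Finally, the numerical illustration rests wholly on assumed rates, and its upper end combines the highest true rate with the lowest control detection. It shows the mechanism and does not forecast what this trial will see.

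**Conclusion.** The point holds as a procedural weakness that is cheap to correct. On the natural reading, RealConsent-F alone gets a triggered staff contact, which may raise detection of distress in the 2-week window and weakens the attention match. On either reading, stopping mid-module triggers nothing. The size cannot be estimated from the documents and may be zero; under the assumed rates the false excess is 2.0 points, range 0 to 6.0.

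A reader might go further and infer that the victimization result is compromised. The documents do not support that: the primary outcome is self-reported by survey in both arms, and nothing here shows its analysis to be wrong. The missing log fields and table would, taken alone, be only missing detail. What makes the change worthwhile is the check-in procedure itself. Confidence is medium, because the key term is ambiguous.

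**What to change.** Amend IV. Safety Considerations so that the same neutrally worded check-in goes to both arms on the same schedule through day 14, whether or not a module is completed. One way is to add a single question to the 48-hour emails, asking whether anything in the program or surveys was upsetting, and to continue those emails for women who have finished or stopped. The project director follows up any positive reply in either arm.

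Record arm and route of detection (check-in, other contact, spontaneous report) in the event log. Add to the Statistical Analysis section a descriptive table, among all randomized women, of the number and percentage with at least one logged event, by arm and source, with a risk difference and 95% confidence interval. If check-ins stay in one arm only, report counts by source and make no between-arm harm claim.

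Costs:
- Up to 14/2 = 7 emails per woman. Those sent after she has finished are new, because the present prompts only remind women to complete modules.
- Staff time for replies. At the assumed rates, true distress alone gives 375 × 0.05 × 0.8 = 15 positive replies per arm (375 × 0.03 × 0.8 = 9 to 375 × 0.10 × 0.8 = 30); other replies would add to this. Staff check-ins after each of the 4 Stress Management modules would instead mean up to 4 × 375 = 1,500 contacts.
- Wording that does not reveal the research question, to which participants are blinded at recruitment.

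The change does not cover distress from the 6-month posttest. It leaves the primary outcome and the sample size as they are.
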